### 3. GENERAL INFORMATION

Objective	To compare binocular visual outcomes with light adjustable lens (LAL) vs. Clareon monofocal/toric IOL when both are targeting mini-monovision (-0.75 ~ -1.00 D in the non-dominant eye).  The hypothesis is that the Clareon monofocal/toric IOL with mini-monovision will provide non-inferior binocular distance vision compared to LAL mini-monovision (non-inferiority margin: 0.1 logMAR).
Test Article(s)	The Clareon™ Monofocal Intraocular Lens (Toric and Non-Toric) The Light-Adjustable Lens™
Sample size	138 subjects total (69 in each group)
Study Population	Age-related Cataract patients with $\geq 0.75$ D corneal astigmatism and without previous experience of monovision $> -1.00$ D offset.
Number of sites	One
Study Design	Single center, multi-surgeon, prospective, randomized, comparative study.
Masking	None.
Variables	Primary: Binocular corrected distance visual acuity (CDVA), 3-months postop.  Secondary: 

• Binocular uncorrected distance visual acuity (UDVA), 3-months postop.

• Binocular distance-corrected intermediate visual acuity (DCIVA) at 66cm, 3-months postop.

• Binocular uncorrected intermediate visual acuity (UIVA) at 66cm, 3-months postop.

• Monocular corrected distance visual acuity (CDVA), 3-months postop.

- Monocular uncorrected distance visual acuity (UDVA), 3-months postop.
- Monocular distance-corrected intermediate visual acuity (DCIVA) at 66cm, 3-months postop.
- Monocular uncorrected intermediate visual acuity (UIVA) at 66cm, 3-months postop.

Exploratory:

- Binocular distance-corrected near visual acuity (DCNVA) at 40cm, 3-months postop.
- Binocular uncorrected near visual acuity (UNVA) at 40cm, 3-months postop.
- Monocular distance corrected defocus curve at 3 months post-op for both eyes in LAL group and dominant eye for Clareon group.
- Binocular defocus curve at 3 months post-op (dominant eye: plano corrected, non-dominant: -1.00D)
- Manifest refraction (MRSE, residual sphere, and residual astigmatism) at postoperative day 17-28 and at 3 months post-op.
- Patient reported spectacle usage questionnaire (PRSIQ) at postoperative day 17-28 and at 3 months post-op
- Total ocular, corneal and internal HOA and SA with iTRACE for both eyes in LAL group and dominant eye for Clareon group (Objective depth of focus measurement with iTRACE for each eyes in both groups)
- Number of days and post-op office visits from cataract surgery to routine "release of care visit" (i.e. final lock-in for LAL group, 17-28 days after 2nd eye surgery for Clareon group).

Duration / Follow-up    Preoperative to 3 months postoperative

## 5. INTRODUCTION

The Light Adjustable Lens (LAL) is claimed to be the first and only intraocular lens (IOL) that can be customized to patient's satisfaction after cataract and IOL implantation surgery by using UV light treatments to adjust the refractive and visual outcomes. LAL allows cataract patients, even those without monovision experience to try mini-monovision and adjust to their visual satisfaction to provide improved range of vision. Clinically, monovision or mini-monovision with monofocal IOLs has been used to provide some presbyopia mitigation, especially before the invention of modern multifocal and extended depth of focus IOLs.

There is limited data on the visual outcomes for patients with mini-monovision with Light Adjustable Lens (LAL) compared to mini-monovision with a traditional monofocal/toric IOL. Previous studies have shown that the Clareon® intraocular lens (IOL) (Alcon, Fort Worth, Texas, USA) provides good visual outcomes for patients at distance. The purpose of this study is to compare binocular visual outcomes with LAL vs. Clareon monofocal/toric IOL when targeting mini-monovision (-0.75 ~ -1.00D).

## 6. OBJECTIVE(S)

To compare binocular visual outcomes with LAL vs. Clareon monofocal/toric IOL when targeting mini-monovision (-0.75 ~ -1.00D).

## 7. SUBJECTS

### 7.1. *Subject Population*

Eligible test subjects will be adult normal astigmatic ( $\geq 0.75$ D corneal astigmatism) cataract patients presenting for cataract surgery who are considered appropriate candidates for intraocular lens implantation.

A total of 138 subjects at one site will be enrolled (69 per group). Both eyes of a subject must be enrolled. Subjects must meet the inclusion criteria. Prior to enrollment, subjects will be provided information on the study and asked to sign a patient information and consent form to participate. The patient information and consent form will be approved by an appropriate ethics committee.

### 7.2. *Inclusion Criteria*

Subjects are eligible for the study if they meet the following criteria:

**Note:** Ocular criteria must be met in both eyes.

- Adult patients undergoing age-related cataract surgery with expected best-corrected visual outcomes of 20/25 or better
- Regular corneal astigmatism of 0.75D-2.50D
- Dilated pupil diameter of 7mm or greater

### 7.3. ***Exclusion Criteria***

If any of the following exclusion criteria are applicable to the subject or either eye, the subject should not be enrolled in the study.

- Moderate-severe corneal pathology, irregular astigmatism, preexisting macular disease and other retinal degenerative diseases that is expected to cause future vision loss, glaucoma, severe dry eye disease, history of uveitis, ocular herpes simplex virus, nystagmus, strabismus, zonular laxity or dehiscence, pseudoexfoliation.
- History of corneal refractive and intraocular surgery.
- Patients taking systemic medication that may increase sensitivity to UV light or that may cause toxicity to the retina.

The principal investigator reserves the right to declare a patient ineligible or non-evaluable based on medical evidence that indicates they are unsuitable for the trial.

Pregnancy has a known effect on the stability of refractions and visual acuity. As such, subjects who become pregnant during the study will not be discontinued but their data may be excluded from analyses of effectiveness.

## 8. STUDY DESIGN

### 8.1. ***Study Design***

This study is a single center, multi-surgeon, prospective, randomized, comparative study of binocular corrected distance visual acuity (CDVA) after successful bilateral cataract surgery. Subjects will be assessed pre-operatively, operatively and at up to 6 post-operative visits. Clinical evaluations will include administration of patient reported spectacle usage questionnaire (PRSIQ), as well as measurement of monocular and binocular visual acuities at distance, intermediate, and near, defocus curve, manifest refraction, measurement of higher order aberrations.

The primary outcome measure will be the binocular corrected distance visual acuity (CDVA), 3-months postop.

Secondary outcome measures are as follows:

- Binocular uncorrected distance visual acuity (UDVA), 3-months postop.
- Binocular distance-corrected intermediate visual acuity (DCIVA) at 66cm, 3-months postop.
- Binocular uncorrected intermediate visual acuity (UIVA) at 66cm, 3-months postop.
- Monocular corrected distance visual acuity (CDVA), 3-months postop.
- Monocular uncorrected distance visual acuity (UDVA), 3-months postop.

- Monocular distance-corrected intermediate visual acuity (DCIVA) at 66cm, 3-months postop.
- Monocular uncorrected intermediate visual acuity (UIVA) at 66cm, 3-months postop.

Exploratory outcome measures are as follows:

- Binocular distance-corrected near visual acuity (DCNVA) at 40cm, 3-months postop.
- Binocular uncorrected near visual acuity (UNVA) at 40cm, 3-months postop.
- Monocular distance corrected defocus curve at 3 months post-op for both eyes in LAL group and dominant eye for Clareon group.
- Binocular defocus curve at 3 months post-op (dominant eye: plano corrected, non-dominant: -1.00D)
- Manifest refraction (MRSE, residual sphere, and residual astigmatism) at postoperative day 17-28 and at 3 months post-op.
- Patient reported spectacle usage questionnaire (PRSIQ) at postoperative day 17-28 and at 3 months post-op
- Total ocular, corneal and internal HOA and SA with iTRACE for both eyes in LAL group and dominant eye for Clareon group (Objective depth of focus measurement with iTRACE for each eyes in both groups).
- Number of days and post-op office visits from cataract surgery to routine "release of care visit" (i.e. final lock-in for LAL group, 17-28 days after 2nd eye surgery for Clareon group).

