### **9.2.3. Postoperative Day 17 to 28**

All routine, usual standard of care postoperative measures should be undertaken. In addition, the subject will undergo VA, manifest refraction, PRSIQ questionnaire, and iTrace testing in accordance with the specifications below (Section 9.3). Adverse events will be monitored.

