### **9.2.5. Postoperative Day 90**

All routine, usual standard of care postoperative measures should be undertaken. In addition, the subject will undergo VA, manifest refraction, defocus curve, PRSIQ questionnaire, and iTrace testing (Section 9.3). Any device deficiencies or adverse events will be monitored.

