##### **10.2.1. Within-treatment Changes**

For variables measured on a continuous scale, these summaries will include the sample size, as well as the mean, standard deviation, median, minimum, and maximum. For variables measured on a categorical scale, summaries will provide the number and percentage of eyes in each category. These summaries will be provided for all eyes completing the study.

Differences between parametric variables will be compared using a two-sample t-test. Differences between categorical variables will be compared using the 2-sample test for equality of proportions.

For non-inferiority testing, if the upper boundary of the 95th confidence interval is not greater than 0.1 logMAR, non-inferiority will be claimed.

The step-down methodology will be used on the non-inferiority endpoints in the following order:

- 1) Binocular CDVA
- 2) Binocular DCIVA
- 3) Binocular UDVA
- 4) Binocular UIVA

The correlation of total ocular and internal HOAs (especially SA) with monocular DCIVA will be evaluated using regression modelling. Findings from these models will provide an indication of whether any HOAs are statistically significantly associated with post-op DCIVA, and the strength of any such association.

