## 15. STANDARD EVALUATION PROCEDURES

**Table 15.1. Proposed Visits and Study Assessments**

(visits are by patient, with both eyes tested)

Activity	Pre-operative	Operative	Postoperative					
	Visit 1	Visit 2a,2b	Visit 3	Visit 4	Visit 5	Visit 6	Visit 7	Visit 8
			POD 17-28	POD 24-42	POD 31-56	POD 38-63	POD 45-70	POD 90
Informed Consent	L,C							
Demographics	L,C							
General Information: Medical History	L,C							
Surgery		L,C						
Manifest refraction	L,C		L,C	L	L	L	L	L,C
Monocular uncorrected distance VA	L,C		L,C	L	L	L	L	L,C
Monocular corrected distance VA	L,C		L,C	L	L	L	L	L,C
Binocular uncorrected and best-corrected distance VA			L,C	L	L	L	L	L,C
Monocular uncorrected and best distance-corrected intermediate VA (66cm)			L,C	L	L	L	L	L,C
Binocular uncorrected and best distance-corrected intermediate VA (66cm)			L,C	L	L	L	L	L,C
Monocular uncorrected and best distance-corrected near VA (40cm)			L,C	L	L	L	L	L,C
Binocular uncorrected and best distance-corrected near VA (40cm)			L,C	L	L	L	L	L,C
Monocular Distance Corrected Defocus Curve								L,C
Binocular Defocus Curve (Dominant eye: plano corrected, non-dominant: -1.00D)								L,C
PRSIQ questionnaire			L,C					L,C
Total ocular, corneal and internal HOA and SA with iTRACE (Both eyes in LAL group and dominant eye for Clareon group)			L	L	L	L	L	L,C
Number of days and post-op office visits from cataract surgery to routine "release of care visit" (i.e. final lock-in for LAL group, 17-28 days after 2nd eye surgery for Clareon group)								L,C
Monitor for Adverse Events and Device Deficiencies		L,C	L,C	L,C	L,C	L,C	L,C	L,C
Complete Exit Form 								L,C

C = Clareon Group; L = LAL group

 Complete Exit Form upon termination of subject participation, or at Visit 8, whichever occurs first.

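### iTRACE depth of focus is listed for every eye in both groups, but Table 15.1 gives it no row, and its only iTRACE row leaves out the Clareon non-dominant eye

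*Combined protocol and SAP*

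**What the plan says.** The synopsis (section 3) and section 8.1 put two iTRACE measures in one exploratory bullet, with different eye sets and no time point:

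- Aberrations: "Total ocular, corneal and internal HOA and SA with iTRACE for both eyes in LAL group and dominant eye for Clareon group".
- Depth of focus, in brackets after it: "Objective depth of focus measurement with iTRACE for each eyes in both groups".

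Table 15.1 has one iTRACE row. It names HOA and SA, not depth of focus, and limits the eyes to "Both eyes in LAL group and dominant eye for Clareon group". It is marked for LAL at Visits 3 to 7 and for both groups at Visit 8 only. The caption of the same table says "visits are by patient, with both eyes tested".

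The visit text is broader than the row. At day 17-28 (section 9.2.3), "the subject will undergo VA, manifest refraction, PRSIQ questionnaire, and iTrace testing", with no limit by group or eye. Section 9.2.5 (day 90) likewise orders iTrace without a limit. Both point to section 9.3 for specifications, but 9.3 covers only refraction, visual acuity, defocus curve and questionnaires.

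The one analysis that names aberrations is in section 10.2.1: "The correlation of total ocular and internal HOAs (especially SA) with monocular DCIVA will be evaluated using regression modelling".

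**The concern.** A coordinator normally works from the assessment table. Followed literally, it gives no instruction to record depth of focus, and the only iTRACE instruction excludes the Clareon non-dominant eye. The listed outcome would then lack half of the Clareon eyes, all of them the eyes set for near-side defocus in a mini-monovision trial. A 3-month reading that is not taken cannot be reconstructed.

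There is a related analysis risk. The two eyes of a subject have different refractive targets, and in the LAL arm they receive different adjustments. From a pre-operative target near +0.25 D (section 9.2.2), reaching -0.75 to -1.00 D is a change of 1.00 to 1.25 D (0.25 + 0.75; 0.25 + 1.00), against 0.25 D for an eye that ends at plano. Section 10.2.1 summarises all eyes completing the study and names a generic two-sample t-test. It gives no rule on which eyes enter and does not mention fellow eyes. Pooling every scanned eye would put non-dominant eyes in the LAL arm only.

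**Working it through.** **Inputs.** 69 subjects per group with both eyes enrolled (section 7.1); eye sets from section 8.1 and Table 15.1. Full enrolment and no dropout are assumed.

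**The plan's own figure.** Section 11 gives 69 per group. With margin 0.1, assumed difference 0.05, SD 0.1, power 90% and one-sided alpha 0.05:

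n = 2 × (1.645 + 1.282)² × 0.1² / (0.1 − 0.05)² ≈ 68.5, rounded up to 69.

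This reproduces the stated figure. It is used here only to count eyes.

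**Eyes required and eyes scheduled for depth of focus**

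| | Required by section 8.1 | Supplied if the Table 15.1 row governs |
|---|---|---|
| LAL dominant | 69 | 69 |
| LAL non-dominant | 69 | 69 |
| Clareon dominant | 69 | 69 |
| Clareon non-dominant | 69 | 0 |
| Total | 276 | 207 |

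Shortfall: 276 − 207 = 69 eyes, which is 69/138 = 50% of Clareon eyes and 69/276 = 25% of all eyes. The dominant-eye comparison is 69 against 69 and the non-dominant comparison is 69 against 0.

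**Day 17-28.** Section 9.2.3 implies iTrace in both groups at Visit 3. Table 15.1 implies LAL only. The two differ for all 69 Clareon subjects.

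**Aberration data as declared.** The HOA/SA set is 138 LAL eyes and 69 Clareon eyes. The non-dominant share is 69/138 = 50% in LAL and 0/69 = 0% in Clareon. If all 207 eyes enter the regression on monocular distance-corrected intermediate acuity (DCIVA), every non-dominant eye is a LAL eye, so any effect of dominance is estimated from LAL subjects alone. The 138 LAL eyes also come from 69 people. With within-person correlation ρ (not given in the documents), for a mean they carry the information of 138/(1 + ρ) independent eyes: 138 at ρ = 0, falling to 69 at ρ = 1.

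**The case against.** The strongest reply is that the eye limit in Table 15.1 belongs to HOA and SA, because that is how the row is labelled. Section 8.1 makes the same split within one bullet. The table caption and section 9.2.5 would both allow each eye to be scanned at day 90. On that reading depth of focus is merely unscheduled. This stands, and it rules out a conclusion that a reader might draw: that the outcome cannot be produced, or that no Clareon non-dominant eye will ever be scanned. The documents do not exclude the scan; they fail to schedule it and leave the question open.

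A reader might also infer that any arm difference in HOA or SA is confounded with eye dominance. The documents do not support that either. The HOA/SA eye sets are stated the same way in the synopsis, section 8.1 and Table 15.1, so the asymmetry is a declared choice. No between-group HOA test is named, and a dominant-with-dominant comparison is available. The problem arises only if eyes are pooled, which the plan neither specifies nor prevents.

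On the regression, it is fair to say that it estimates an association and not an arm contrast, that unequal eye counts do not by themselves bias it, and that distance correction is meant to take the different refractive targets out of DCIVA. What remains is the absence of any statement on dominance or on paired LAL eyes.

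Finally, all of this is exploratory and outside the step-down sequence. That is correct, and it sets the severity.

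**Conclusion.** The inconsistency is real and its consequence is conditional. If the single iTRACE row governs, depth of focus is missing for 69 of 276 eyes, all Clareon non-dominant, and the non-dominant comparison has no Clareon data. The dominant-eye comparison is intact. Separately, section 9.2.3 and Table 15.1 disagree on whether Clareon subjects have iTrace at day 17-28, and section 9.3 contains nothing that settles either question.

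The counts assume 69 subjects per group with no dropout; they measure missing data, not bias. The primary and secondary endpoints are unaffected. Severity is low. The case for acting is that the correction is cheap and the data are lost after Visit 8.

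**What to change.** 1. Add a row to Table 15.1 for iTRACE depth of focus at Visit 8, both eyes, both groups.
2. Make sections 9.2.3 and 9.2.5 and Table 15.1 agree on which groups and eyes have iTrace at each visit, including whether Clareon subjects are scanned at Visit 3.
3. Leave the HOA/SA eye sets as declared if the sponsor wishes, but state in section 10.2.1 that any between-group comparison of HOA, SA or monocular defocus is dominant eye with dominant eye.
4. State that the HOA-DCIVA regression accounts for eye dominance and for two eyes per LAL subject, for example with a dominance term and a subject random effect or subject-clustered standard errors.

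The cost is one table row and a few sentences, plus one additional iTrace reading per Clareon subject (69 in all), which the outcome list already implies.

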### ***8.2. Methods Used to Minimize Bias***

Patient selection will be based on the patient's interest and the surgeon's opinion as to whether they are a suitable candidate for IOL implantation. Subjects will be randomized to treatment groups.

The measurement of visual acuity will be conducted in a systematic fashion to minimize bias. Individuals conducting visual acuity measures will be instructed to perform the same testing in the same fashion for all subjects, with the same level of encouragement to subjects. Questionnaire instructions will be provided to all patients in a similar manner.

All data collection will be completed through provided Case Report Forms (CRFs) or computer files generated by automated test equipment. All site personnel involved in the study will be trained in regard to conducting study-specific procedures.

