### **9.3.1. Manifest Refraction**

Perform a manifest refraction with a high contrast logMAR chart under photopic lighting conditions ( $>85\text{ cd/m}^2$ ). Document refraction results with sphere, cylinder and axis readings. If uncorrected visual acuity is not improved by manifest refraction, use zero for sphere and cylinder and draw a line through the blank for the axis.

***Note:*** Each subject should be manually refracted to his/her best correction by an ophthalmologist, optometrist, or a skilled technician using a phoropter or trial lenses.

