### **9.3.2. Visual Acuity (VA)**

To obtain logMAR VA, ask subjects to begin reading the chart at the smallest row where all letters are easily distinguishable. Have subjects continue to read rows with smaller letters and encourage subjects to guess at all letters in a line if at least one correct response was given on the previous row. Request subjects read rows until no letters on a row are read correctly or until all letters on a row are too indistinguishable to even be guessed.

While the subject is reading the chart, record the number of letters on each line read incorrectly by the subject. The last line from which the subject read at least one letter correctly is recorded as the baseline logMAR VA. The actual logMAR VA is calculated using the baseline logMAR VA line and the number of letters read incorrectly.

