#### *Distance VA*

Measure distance visual acuity using a high contrast logMAR ETDRS chart under photopic lighting ( $>85 \text{ cd/m}^2$ ) at a distance of 4 m.

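### Nothing in the plan keeps the Visit 8 acuity examiner unaware of the lens, although the primary endpoint depends on subjective refraction and encouraged guessing; a cheap partial mask is available

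*Combined protocol and SAP*

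**What the plan says.** Section 3 gives the masking as none. The only blinding mentioned anywhere is that of the biostatistician at the interim sample size re-estimation (section 11).

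The primary endpoint is binocular CDVA at 3 months (sections 3 and 8.1). Two steps in measuring it depend on the examiner and the subject:

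- Refraction (9.3.1): "Each subject should be manually refracted to his/her best correction by an ophthalmologist, optometrist, or a skilled technician".
- Acuity (9.3.2): the examiner is to "encourage subjects to guess at all letters in a line if at least one correct response was given on the previous row", and the score counts letters: "The actual logMAR VA is calculated using the baseline logMAR VA line and the number of letters read incorrectly".

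The protection is standardisation. Section 8.2 says: "Individuals conducting visual acuity measures will be instructed to perform the same testing in the same fashion for all subjects", and continues "with the same level of encouragement to subjects". It also requires training of site personnel. Section 9.3.2 scripts the starting row, the guessing rule and the stopping rule. The distance test has a fixed chart, lighting and viewing distance ("Measure distance visual acuity using a high contrast logMAR ETDRS chart under photopic lighting", at 4 m).

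Section 9.2.5 lists the Visit 8 tests but does not make the list an order of testing, and it does not say who performs them.

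**The concern.** Equal encouragement is an instruction to the examiner; it does not remove knowledge of the arm. An examiner who knows the lens can, without intending to, refine the refraction a little longer or press for one more letter in one arm. Section 8.2 itself names encouragement as something to be held equal, so the plan recognises the route.

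An examiner effect common to both arms cancels in the comparison. A differential effect does not: it is added directly to the mean difference that is compared with the 0.1 logMAR margin. If it favours Clareon, the lens to be shown non-inferior, it raises the chance of a false claim. If it favours LAL, it costs power. A larger sample does not remove it.

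Subjects and surgeons cannot practicably be masked, because only LAL subjects attend for UV treatment and lock-in. The person who refracts and reads acuity at Visit 8 is a separate matter.

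**Working it through.** **Inputs from the documents.** Margin 0.1 logMAR (section 3); assumed difference 0.05, pooled SD 0.1, 69 per group, power 90%, alpha 0.05 (section 11); non-inferiority is claimed if the upper 95% confidence limit does not exceed 0.1 (section 10.2.1). Neither section 10 nor section 11 states whether the interval or alpha is one-sided or two-sided.

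**Assumptions.** Five letters per 0.1 logMAR line, so one letter = 0.02 and half a letter = 0.01. The documents name the ETDRS chart but do not print the letter value. The shifts b = 0.01 and 0.02 are scenarios: each is an average difference between arms caused by the examiner.

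**1. The plan's sample size.** n per group = 2 × [SD × (z(1−α) + z(0.90)) / (0.1 − 0.05)]².

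- One-sided α = 0.05: 2 × [0.1 × (1.645 + 1.282) / 0.05]² = 68.5, so 69. This matches.
- One-sided α = 0.025 (two-sided 95% interval): 2 × [0.1 × (1.960 + 1.282) / 0.05]² = 84.1, so 85. This does not match.

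Both readings are therefore carried forward.

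**2. Standard error.** 0.1 × √(2/69) = 0.01703 logMAR. A half-letter shift is 0.01/0.01703 = 0.59 SE; a one-letter shift is 1.17 SE.

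**3. False-claim rate at a true difference of 0.10, shift b towards Clareon.** The normal approximation is Φ(−z(1−α) + b/SE). For example, with α = 0.025 and b = 0.02: Φ(−1.960 + 1.175) = 0.216. The table uses the noncentral t with 136 df.

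| Shift towards Clareon | Two-sided 95% CI (one-sided 0.025) | One-sided 95% bound (0.05) |
|---|---|---|
| 0 | 0.0250 | 0.0500 |
| 0.01 | 0.0843 | 0.1445 |
| 0.02 | 0.2137 | 0.3171 |

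A simulation of 200,000 trials gave 0.084 and 0.213 in the first column, and 0.144 and 0.318 in the second.

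**4. Power at a true difference of 0.05, shift of 0.02 towards LAL** (apparent difference 0.05 + 0.02 = 0.07), noncentral t.

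| | One-sided 0.025 | One-sided 0.05 |
|---|---|---|
| No shift | 0.830 | 0.899 |
| 0.02 towards LAL | 0.417 | 0.543 |

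The starting power of 83% in the first column comes from the sidedness question in step 1, not from masking.

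**5. Sensitivity to SD**, assumed range 0.05 to 0.15, n = 69, true difference at the margin, noncentral t.

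| Shift towards Clareon | One-sided 0.025 | One-sided 0.05 |
|---|---|---|
| 0.01 | 21.4% down to 5.8% | 31.7% down to 10.5% |
| 0.02 | 64.5% down to 11.9% | 75.6% down to 19.3% |

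The rate at least doubles in every case.

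**6. Larger sample.** At 85 per group, SD 0.1 and one-sided 0.025, the rates are 9.5% and 25.4%, slightly worse than at 69, because the SE shrinks and the bias does not.

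**7. Other true differences.** If the true difference is 0.12, a one-letter shift towards Clareon only brings the false-claim rate back to the nominal 2.5% or 5%. At the margin, a shift towards LAL makes the rule conservative: at one-sided 0.025, half a letter gives about 0.5% and one letter about 0.1%.

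**The case against.** The open-label design is stated openly, and no section gives evidence that an examiner effect exists, how large it is or which way it runs. The same calculation would apply to any unmasked acuity trial of this size. The existing safeguards amount to more than one instruction: equal encouragement, training, a scripted reading procedure and a fixed chart all address this route. All of that stands. It limits the point to sensitivity and a missing safeguard; it does not supply the safeguard.

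Three stronger readings are tempting and should not be adopted.

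- **That examiners do know the lens, and that this favours Clareon.** Their knowledge is inferred from the absence of masking; the plan does not say it. Direction is not stated at all.
- **That the Visit 8 tests themselves give the arm away.** Table 15.1 limits the iTrace aberration measurement ("Both eyes in LAL group and dominant eye for Clareon group"), and sections 3 and 8.1 limit the monocular defocus curve in the same way. But those sections also call for iTrace depth of focus in each eye of both groups, and Table 15.1 puts no eye restriction on the defocus curve. The defocus procedure needs the manifest refraction in place, so refraction already comes before it. Unmasking by procedure is possible, not established.
- **That anyone who saw the subject at Visits 3 to 7 should be barred from Visit 8.** Only LAL subjects attend Visits 4 to 7 (Table 9.2-1), so this rule would exclude more examiners for LAL and tie examiner identity to arm.

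Staffing is also unknown. The plan speaks of examiners in the plural and lists three eligible staff types, but gives no headcount. Masking can therefore be asked for only where feasible.

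**Conclusion.** The point holds as a gap in bias control for the primary endpoint. The plan standardises acuity testing but takes no step to keep the Visit 8 examiner unaware of the lens. The trial's conclusion is sensitive to small differential shifts: under the stated assumptions, half a letter to one letter towards Clareon multiplies the false-claim rate at the margin by about 3.4 to 8.5 (two-sided interval) or 2.9 to 6.3 (one-sided bound). One letter towards LAL removes 36 to 41 percentage points of power at the planned difference.

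These figures rest on the assumed letter value, on SD 0.10 with 69 per group, on a shift that is differential between arms and, for the false-claim rates, on a true difference exactly at 0.1. They show what such a shift would do. They are not an estimate of bias in this trial. The trial can run as written; the change is worth making because it is cheap now and the readings cannot be repaired later.

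**What to change.** 1. In section 3, change the masking entry to: Visit 8 acuity examiner masked where feasible.
2. In section 9.2.5, require manifest refraction and all acuities to be completed before the defocus curve and iTrace.
3. Leave lens type off the Visit 8 acuity worksheet, and ask subjects not to mention it to the examiner.
4. Draw the Visit 8 examiners for both arms from one common pool of existing trained staff, where feasible staff who do not work the LAL UV and lock-in visits, so that examiner identity is not tied to arm.
5. On CRF 8, record the examiner ID and whether the examiner knew the arm. Prespecify a sensitivity analysis of binocular CDVA using these items.

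The cost is some rota planning and two CRF items, with no added test and no change to treatment or sample size. Masking will sometimes fail, which item 5 documents. Effort driven by the subject stays unmasked whatever is done.
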